#### **11.4. One-Month Follow-up Visit**

At thirty (30) +/- 7 days following device system implant, study subjects must participate in an in office One-Month Follow-up Visit. A full device system evaluation must be performed during this visit as well as a check for adverse events since implant. The following study subject data must be collected during the One-Month Follow-up Visit:

- Measurements regarding the 4-SITE Lead/Header System; and, for the RV lead, the following:
  - Amplitude (sensing);
  - Impedance (shock and pacing); and
  - Voltage pacing threshold (record pulse width used).
- 4-SITE Lead/Header System-related Adverse Events; and
- The presence/absence of adverse events identified during active study subject medical record review.

Upon device interrogation, if observed values show evidence of suspected lead/device malfunction, a chest radiograph(s) to determine lead position is strongly recommended, but at the discretion of the Investigator. If noise is detected in the intracardiac electrogram (EGM) storage, techniques such as pocket manipulation, arm maneuvers, valsalva maneuver, coughing and/or exploration of potential sources of external magnetic interference (EMI) may be used to detect system abnormalities, at the discretion of the Investigator.

Study subject data collected during the One-Month Follow-up Visit must be promptly entered into the BSC electronic data capture system. Source documentation must be maintained by the center in the study files. Where copies of original source documents as well as printouts of original electronic source documents are retained, these shall be signed and dated by a member of the investigational site/center team with a statement that they are a true reproduction of the original source documents.

#### **11.5. Bi-Annual Study Subject Follow-up Visits**

The study subject's implanted device system must be evaluated on a regular basis at the investigational site's facility. An implanted device system interrogation must take place bi-annually (*i.e.*, every six months +/- 30 days) following the device system implant for a period

of five (5) years. All study follow-up visit dates are based on days from the device system implant. The dates for the follow-up visits are listed in Table 11-1 above.

A full device system evaluation must be performed during this visit at the investigational site's facility as well as a check for any adverse events occurring since implant. The following study subject data must be collected during all Bi-Annual Study Subject Follow-up Visits:

- Measurements regarding the 4-SITE Lead/Header System; and
  - Amplitude (sensing);
  - Impedance (shock and pacing);
  - Voltage pacing threshold (record pulse width used); and
  - 4-SITE Lead/Header System-related adverse events.
- The presence/absence of adverse events identified during active study subject medical record review.

Follow-up visit data must be promptly entered into the BSC electronic data capture system. Source documentation must be maintained by the investigational site/center personnel in the study files. Where copies of original source documents as well as printouts of original electronic source documents are retained, these shall be signed and dated by a member of the investigational site/center team as confirmation that they are a true reproduction of the original source documents.

#### **11.5.1. Missed Bi-Annual Study Subject Follow-Up Visits**

In the event that a Bi-Annual Study Subject Follow-Up Visit is missed, investigational site/center personnel are expected to make every effort to contact the study subject (*e.g.*, via certified mail, telephone calls, Email messages, etc.) in order to determine the subject's status. Study subjects are considered "lost-to-follow-up" after three (3) documented contact attempts and should be immediately withdrawn from the study if investigational site/center personnel have not had any contact with a study subject after three attempts. The date of the study subject's last in-clinic follow-up visit (scheduled or unscheduled) will be used as the date that he/she was "lost-to-follow-up" and therefore ended their participation in the study. Study subjects will be withdrawn at any time if they express their desire to cease their participation in the study.

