## 10. Subject Accountability

### 10.1. Point of Enrollment

At enrollment, the Informed Consent form must be completed and signed/dated by the subject (or signed/dated by a legally authorized representative). Subjects who meet all of the inclusion criteria and none of the exclusion criteria, and who have signed an Informed Consent form, are considered enrolled in the study and will count toward the study enrollment ceiling. Patients may be consented only one time for this protocol and can only be enrolled with their initial implant of a 4-SITE lead. Even if an enrolled study subject is subsequently determined to be an *attempt* or *intent* with respect to the implantation of a device system (see Sub-section 11.5.2), he/she will be counted toward the study enrollment ceiling. *Attempt* subjects shall be withdrawn from participation in the study after collection of any potential 4-SITE Lead/Header System related adverse events. The original Informed Consent form and any screening documentation for *intent* subjects should be maintained in the center's administrative study files.

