## 10.2. Point of Study Exit

All subjects enrolled in the clinical study (including those withdrawn from the clinical study or lost to follow-up) shall be accounted for and documented. Study subjects can exit the study for the following reasons: study completion (subject completed 5 years of follow-up), death, or withdrawal. If a subject withdraws from the clinical investigation, the reason(s) shall be reported.

Reasons for withdrawal include, but are not limited to: adverse event, Investigator discretion, Lost to follow-up, RV lead no longer in service, transplant or removal of target organ, or subject withdrew from participation in study. While study withdrawal is discouraged, subjects may withdraw from the study at any time, with or without reason, and without prejudice to further treatment. All applicable case report forms up to the point of subject withdrawal and an "End of Study" form must be completed. Subjects who are "lost-to-follow-up" should have documented attempts to contact them prior to completion of the "End of Study" form.

Additional data may no longer be collected after the point at which a subject has been withdrawn from the study or withdraws his/her consent, for whatever reason. All open adverse events should be closed or documented as chronic. Data collected up to the point of study subject withdrawal may be used.

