**13.3.9. End of Study Case Report Form**

An End of Study Case Report Form will be completed when a study subject is no longer active in the LSS of 4-SITE Study. Reasons for a change in study subject status include study completion, death and withdrawal.

The status of the 4-SITE lead must be reported at the time of subject withdrawal from the study.

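### One missed bi-annual visit plus three unanswered contacts leads to immediate withdrawal and a bar on later data, so recoverable follow-up and late-learned events are lost; if loss is related to lead events, the complication-free rate is biased upward

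*Combined protocol and SAP*

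**What the plan says.** Section 11.5.1 applies once a bi-annual visit is missed. Site staff "are expected to make every effort to contact the study subject" and establish the subject's status. The threshold follows: "Study subjects are considered 'lost-to-follow-up' after three (3) documented contact attempts". Such subjects "should be immediately withdrawn from the study if investigational site/center personnel have not had any contact with a study subject after three attempts". No interval between attempts, minimum elapsed time or second missed visit is required. The "last in-clinic follow-up visit (scheduled or unscheduled) will be used as the date" of loss.

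Section 10.2 lists loss to follow-up among the reasons for withdrawal and states: "Additional data may no longer be collected after the point at which a subject has been withdrawn from the study". The bar covers withdrawal for any reason, so a subject who could not be reached is treated like one who revoked consent. Section 10.1 adds: "Patients may be consented only one time for this protocol". No section describes how a subject could re-enter.

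Under Section 12.3.1, lost subjects are censored in the Kaplan-Meier analysis. Sections 12.3.1 to 12.3.4 give no sensitivity analysis for loss related to the endpoint.

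There are safeguards. Section 13.1 requires active record review for events during and between visits. Section 10.2 requires all applicable forms up to withdrawal. Section 13.3.9 states: "The status of the 4-SITE lead must be reported at the time of subject withdrawal from the study".

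**The concern.** Subjects join intending to stay with their investigator for five years (Section 9.2), so some who miss one visit may well come back. The rule ends their participation for a reason that may be temporary, and Section 10.2 prevents recovery of what the chart would show on return. This sits awkwardly with the rest of the protocol: Section 20.3 runs adverse event reporting through the five-year period, and Section 22.5 keeps subjects at a terminated center in follow-up for the full five years where possible.

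The primary result is one Kaplan-Meier estimate compared with a fixed goal, with no control arm to share the loss. If a lead event makes a subject more likely to miss a visit and go unreached, endpoint events drop out more often than event-free intervals. The estimate then moves toward success.

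**Working it through.** **Does the plan give a figure to reproduce?** No. The loss rate, assumed true rate and power are not visible, because the sample-size parameters are redacted in Section 12.1.4 and the synopsis. What follows is a reading of the rule plus illustrations under stated assumptions.

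**1. Unobserved time removed.** From the visit table in Section 11.1.1, the 6-month visit may fall as early as day 180 − 30 = 150, and the 12-month window closes on day 365 + 30 = 395. If the 12-month visit is missed, the back-dated exit can precede the close of that window by 395 − 150 = 245 days, plus the contact period. An unscheduled in-clinic visit shortens this gap.

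**2. Number the rule could touch.** Assume a chance m per visit of being missed and not reached, over 10 bi-annual visits. The proportion retained is (1 − m)^10.

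| m (assumed) | Retained | Exits among 1,780 |
|---|---|---|
| 1% | 90.4% | 170 |
| 2% | 81.7% | 326 |
| 3% | 73.7% | 467 |

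These are subjects who would meet the rule, ignoring events and other exits. Some would be lost under any rule, so the figures are not the excess caused by this one.

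**3. Bias if loss is related to events.** Let R be the true five-year risk and h = 1 − (1 − R)^(1/10) the risk per interval. Let m be the chance of loss in an event-free interval and e the chance in the interval containing an event. A lost subject is censored at the previous visit and contributes nothing to that interval, so the observed interval risk is

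h′ = h(1 − e) / [h(1 − e) + (1 − h)(1 − m)],

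and the observed five-year risk is 1 − (1 − h′)^10.

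With R = 5%, h = 0.005116. Taking m = 2% and e = 10%: h′ = 0.004605 / (0.004605 + 0.974986) = 0.004701, which gives 4.6%.

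| True risk R | m | e | Observed risk |
|---|---|---|---|
| 5.0% | 2% | 2% | 5.0% |
| 5.0% | 2% | 10% | 4.6% |
| 5.0% | 2% | 20% | 4.1% |
| 5.0% | 2% | 30% | 3.6% |
| 8.0% | 2% | 20% | 6.6% |

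The first row is the control: equal loss gives no bias. In the last row the true complication-free rate is 92.0%, below the goal, but it is observed as about 93.4%.

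**4. Effect on the decision.** With no censoring and a Wald lower one-sided 95% bound, 1,780 subjects can have at most 116 events and still pass: 93.48% − 1.645 × √(0.9348 × 0.0652 / 1,780) = 92.52%. With 117 events the bound is 92.46%. A modest number of missed events could therefore change the result.

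A simulation of 10 intervals used N = 1,780, the Greenwood bound, m = 2% and a true rate of exactly 92.5%. The study passed in about 6% of runs with equal loss, and in about 11%, 24% and 70% when e was 5%, 10% and 20%. A separate simulation that hid a fixed share of events gave 5–6% with none hidden, 28–32% with 10% hidden and 67–80% with 20% hidden. In that simulation, back-dating loss that was independent of events left the estimate at about 92.5%.

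**The case against.** The strongest reply is that an event is lost only through a chain of failures. The visit must be missed despite a 60-day window, every contact attempt must fail, and neither the record review (Section 13.1), the forms due up to withdrawal (Section 10.2) nor the lead-status report (Section 13.3.9) may reveal it. An event found before exit can be entered. Dating loss to last confirmed status is also sound practice, because it credits no unobserved time.

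Much of this stands, and it rules out four stronger readings that a reader might infer:

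- **That withdrawal is compulsory and irreversible.** Section 11.5.1 says subjects should be withdrawn. The one-consent sentence in Section 10.1 goes on to tie enrollment to the initial lead implant, so it guards against duplicate enrollment and does not address return under the original consent. The documents are silent on re-entry; they do not forbid it by name.
- **That every subject with a lead event elsewhere is counted as complication-free.** A censored subject counts as event-free only to the last in-clinic visit, and only if the safeguards fail.
- **That lead status cannot be reported for these subjects.** Chart review may supply it. The protocol simply names no source for a subject nobody has reached.
- **That back-dating is itself biased.** It is not; bias needs event-related loss.

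The safeguards still leave a gap. The visit table schedules chart review at visits, the examples in Section 13.1 are implant, discharge and in-office visits, and no step obtains outside records. No rule says whether an event dated between the last visit and withdrawal counts. Nothing before exit helps with an event learned of afterwards.

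**Conclusion.** The point holds as a design weakness with a conditional effect. Followed as written, the rules end follow-up after one missed visit and three closely spaced failed attempts, and then exclude later data from subjects who never withdrew consent. The loss of recoverable follow-up follows from the text.

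Upward bias follows only if loss is related to lead events that contact attempts and chart review miss; otherwise the cost is precision. The observed risk of 4.6% to 3.6% against a true 5.0% rests on assumed loss of 2% per visit otherwise and 10–30% in the interval containing an event. Those rates are not document figures. The calculation gives no credit for events recovered by chart review and makes no comparison with another rule, so it shows direction and sensitivity, not an expected error. The change is worth making because it is cheap and protects the five-year estimate.

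**What to change.** **Section 11.5.1.** Treat a missed bi-annual visit as a deviation and keep the subject enrolled. Require the three attempts on separate dates, at least one in writing. Finalise lost-to-follow-up only after a longer unreached period or at study closure. Waiting until the next scheduled window is also missed is one reasonable threshold; the exact choice is open. Before the End of Study form, complete the chart review already required by Section 13.1 and the lead-status report required by Section 13.3.9.

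**Section 10.2.** Limit the bar on further data to subjects who withdrew consent. Let a subject who returns before study closure resume under the original consent. State that endpoint events found after the last in-clinic visit are entered and adjudicated at their actual date. Restore event-free time by the same rule for subjects who return without an event; recovering events alone would bias the estimate downward.

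**Cost.** One rewritten paragraph in 11.5.1 and matching text in 10.2, some extra contact effort and more missed-visit deviations. No additional subjects or study procedures are needed.

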#### **11.6. *Unscheduled Follow-Up Visits***

Unscheduled Follow-up Visits occurring between regularly scheduled study visits are intended to collect information on adverse events, or in response to a sponsor-requested visit.

NOTE: For visits where device reprogramming is completed, or other regular interim visits not required by the study (i.e. optimization of programmed settings); this information is not required to be reported on an *Unscheduled Follow-Up Form*.

## **11.7. Study Completion**

Study subjects should expect data collection to last five (5) years from the index device system implant or if BSC has officially terminated/closed the study. After a subject has completed his/her last scheduled bi-annual visit (at five years post implant) or the study has been terminated, their participation in the study is complete. Subsequent to the completion of this last visit and the recording of any adverse events, the subject will no longer be considered enrolled in the study and all parameters regarding the implanted device system may be managed at the discretion of a qualified investigator. An “End of Study Form” is required to be completed, whenever a study subject exits the study (regardless of timing).

## **12. Statistical Considerations**

### **12.1. Primary Study Endpoint**

The primary LSS of 4-SITE Study endpoint is the “chronic 4-SITE Lead/Header System-related complication-free rate”.

#### **12.1.1. Description and Rationale for Endpoint Selection**

The 4-SITE Lead/Header System will be evaluated based on the “chronic 4-SITE Lead/Header System-related complication-free rate” for the five (5) year follow-up period after the index implantation. The primary endpoint analysis will include confirmed 4-SITE Lead/Header System-related complications that result in permanent loss of therapy, invasive intervention, injury or death.

#### **12.1.2. Endpoint-related Adverse Events**

Inclusion of adverse events in the endpoint is based on the adjudication of the adverse event by the independent Clinical Events Committee (CEC), and on the time of occurrence of the adverse event.

The following adverse events will all be reported, and those adverse events that result in permanent loss of therapy, invasive intervention, injury or death will be included in the endpoint analysis regardless of cause or time of occurrence:

- Pneumothorax;
- Perforation; and
- Cardiac tamponade.

The following adverse events, occurring at 30 days or less from lead-related surgery, will all be reported, and those adverse events that result in permanent loss of therapy, invasive intervention, injury or death and that are also determined to be attributable to a structural lead/header failure by the Clinical Events Committee (CEC) will included in the endpoint analysis:

- Right ventricular lead dislodgment;

- Extra-cardiac (diaphragmatic/pectoral) stimulation caused by the RV lead;
- Inability to place or position the right ventricle (RV) lead;
- Implant procedure-related complications such as arrhythmias and hematoma formations;
- Infection;
- In-patient damage to RV lead (*e.g.*, accidental cut to lead body during pocket revision, device replacement, etc.);
- Other procedure-related adverse events identified at implantation;
- Lead under-insertion identified at implant; and
- Loose header set screws identified at implant.

The following adverse events, occurring more than 30 days after lead-related surgery, will all be reported, and those adverse events that result in permanent loss of therapy, invasive intervention, injury or death will be included in the endpoint analysis for the 4-SITE Lead/Header System:

- Right ventricular lead dislodgment;
- Extra-cardiac (diaphragmatic/pectoral) stimulation caused by the RV lead;
- Low/High impedance values; and
- High right ventricle (RV) pacing threshold with sudden change (>2 volts), intermittent RV capture and non-capture of the RV lead.

The following adverse events, occurring more than 30 days after lead-related surgery, will all be reported, and those adverse events that result in permanent loss of therapy, invasive intervention, injury or death and that are determined to be attributable to a structural 4-SITE Lead/Header System failure by the Clinical Events Committee will be included in the endpoint analysis. Examples of events which will be sent to the Clinical Events Committee are listed below. Many of these may be adjudicated by the Clinical Events Committee to be unrelated to malfunction of the 4-SITE Lead/Header System,

- Lead/Header connection-related adverse events in systems not tested using a high- or maximum-energy ventricular tachyarrhythmia conversion test;
- RV lead-related thrombosis;
- Twiddler's syndrome (*i.e.*, permanent malfunction of a pacemaker due to the patient's manipulation of the pulse generator in the implant pocket) leading to RV lead dislodgment;
- Infection;
- Atrial lead, CRT lead or generator adverse events requiring additional interventions;
- RV lead-related hospitalizations;
- Death;
- Lead revisions to optimize therapy;

- Exit block or failure to capture (*i.e.*, delay or failure of an impulse to be conducted from a specific region to surrounding tissues);
- Physiologic over-sensing or under-sensing;
- Non-physiologic over-sensing from an unidentifiable cause;
- Lead under-insertion identified at implant; and
- Loose header set screws identified at implant.

Regardless of endpoint inclusion, all reportable adverse events will be collected and reported during the conduct of the LSS of 4-SITE Study. For further explanation, see the definition of common adverse events presented in the Potential Risk and Benefits Section 18.

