## 7. Study Endpoints

The 4-SITE Lead/Header System will be evaluated based on the “chronic 4-SITE Lead/Header System-related complication-free rate” for the five (5) year follow-up period after the index implantation. The primary endpoint analysis will include confirmed chronic 4-SITE Lead/Header System-related complications that result in study subject permanent loss of therapy, invasive intervention, injury or death. Investigator and study subject induced device dysfunctions (*e.g.*, Twiddler’s Syndrome and inadvertent cutting of lead insulation during the implantation procedure) will be recorded, but will not be included in the study endpoint analysis.

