## **12.3. Data Analyses**

### **12.3.1. Primary Study Endpoint Analysis**

Regarding the 4-SITE Lead and the compatible header in a PG, the primary study endpoint is the evaluation of the proportion of subjects without a chronic 4-SITE Lead/Header-related complication within five (5) years post-implant period. When the final study subject reaches five (5) years of follow-up, the primary analysis will be performed based on the Kaplan-Meier method for the estimation of the five (5) year chronic lead-related complication-free rate, including the lower one-sided 95% confidence interval. The censoring mechanism of the Kaplan-Meier analysis incorporates all available data on study subjects, including those that withdrew or were lost-to-follow-up.

The Kaplan-Meier analysis will begin at the time of implant for each study subject. All subjects who are successfully implanted with the 4-SITE Lead/Header System will be included in the analysis. The endpoint adverse events are defined as complications meeting the criteria described in Sub-section 12.1.2 above. The determination for inclusion of adverse events in the endpoint analysis will be made by an independent Clinical Events Committee (see Sub-section 22.1 hereinafter). Additionally, since this study is focused on chronic 4-SITE Lead/Header System performance, except as noted in Sub-section 12.1.2

above, acute adverse events associated with attempted lead implants will not be included in this analysis. These events fall within the 30 days of an invasive cardiac surgery and do not meet the criteria outlined in Sub-section 12.1.2 above.

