### **12.3.2. Additional Analyses/Changes to Planned Analyses**

In addition to the primary endpoint analysis, the adverse events contributing to the endpoint will be analyzed. The individual adverse event rates and 95% upper confidence bounds will be provided.

Any changes to the planned statistical analyses made prior to performing the analyses will be documented in an amended Statistical Analysis Plan approved prior to performing the analyses. Changes from the planned statistical methods after performing the analyses will be documented in the clinical study report along with a reason for the deviation.

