### **18.3. Potential Lead Implantation Adverse Events**

Potential adverse events from implantation of a lead system include, but are not limited to, the following: allergic/physical/physiologic reaction; death; erosion or migration; fibrillation or other arrhythmias; lead or accessory breakage (fracture/insulation/lead tip); hematoma or seroma; inappropriate or inability to provide therapy (shocks/pacing/sensing); infection; procedure related; and component failure. In rare cases severe complications or device failures can occur.

Table 18.2-1: Some Examples of Possible Causes for Reportable Adverse Events

PG-Related	RA Lead-, RV Lead-, or LV Lead and Accessories-Related	Header-Related	Physician & Subject-Related (Non-Device System-Related)

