
 
Accelerated arrhythmia episode (ventricular)
 
Inability to deliver shock or pace therapy
 
Inappropriate shock/therapy (e.g., shocks, ATP, pacing)
 
Migration of pulse generator
 
Pectoral muscle stimulation
 
Possible malfunction (e.g., premature battery depletion)
 
PG-related adverse event requiring additional interventions
 
Post-shock rhythm disturbances
 
Pulse generator fault code detected
 
Skin erosion
 
Oversensing, undersensing, noise
 
Other PG-related, please specify
 
	
 
Cardiac perforation /tamponade
 
Lead dislodgement
 
Elevated thresholds
 
Extra-cardiac stimulation (e.g., phrenic, diaphragm)
 
High or low pacing impedance
 
High or low shock impedance
 
High or low shock impedance when attempting to deliver a shock
 
Inability to place lead
 
In-subject damage to RV lead
 
Inappropriate shock due to over-sensing
 
Intermittent sensing
 
Lead revisions to optimize therapy
 
Loss of capture
 
Pacing impedance changes
 
RA or LV lead-related adverse event requiring additional intervention(s)
 
RV lead-related thrombosis
 
Shock impedance changes
 
Oversensing, undersensing, noise
 
Suspected lead fracture
 
Suspected lead abrasion
 
Lead insulation breach
 
Header/connector problem
 
Subclavian lead crush damage
 
Other lead or accessories-related, please specify
 
	
 
Difficulty with placing existing lead
 
Difficulty with placing new lead in header
 
Difficulty with removing lead from header
 
Difficulty with tightening set screw
 
Elevated thresholds
 
High pacing impedance
 
High shock impedance
 
High shock impedance when attempting to deliver a shock
 
Inability to deliver shock or pace therapy
 
Inappropriate shock
 
Loose set screws identified at implant
 
Loss-of-capture
 
Low pacing impedance
 
Low shock impedance
 
Pacing impedance changes
 
Shock impedance changes
 
Significant r-wave amplitude decrease during two (2) weeks or less
 
Oversensing, undersensing, noise
 
Other header-related, please specify
 
	
 
Hematoma
 
Pain
 
Pneumothorax
 
Twiddler's Syndrome
 
Infection
 
Allergic reactions
 
Drug reactions
 
Implant procedure related complications (i.e arrhythmias and hematoma)
 
Lead under-insertion identified at implant
 
Non-RV lead-related death
 
Non-RV lead-related hospitalization(s)
 
Other procedure-related adverse events identified at implant, please specify
 
 
NOTE:
 
Physician and study subject induced injury will be recorded, but will not be included as adverse events in the endpoint analysis of the study (e.g., auto accident causing lead/header dysfunction, or inadvertent cutting of lead insulation by physician during the implantation procedure).

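### The Table 18.2-1 note excludes physician-induced injury from the endpoint without exception, while Section 12.1.2 counts pneumothorax, perforation and tamponade whatever the cause: a minor wording conflict to reconcile

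*Combined protocol and SAP*

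**What the plan says.** **Section 12.1.2** names three events (pneumothorax, perforation and cardiac tamponade). Where one of them leads to lasting loss of therapy, an invasive procedure, injury or death, it "will be included in the endpoint analysis regardless of cause or time of occurrence".

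**Section 12.3.1** ties the analysis to that list: "The endpoint adverse events are defined as complications meeting the criteria described in Sub-section 12.1.2 above". It also says who decides: "The determination for inclusion of adverse events in the endpoint analysis will be made by an independent Clinical Events Committee".

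**Table 18.2-1** (printed under Section 18.3) lists pneumothorax in its fourth column, which holds physician- and subject-related causes and is labelled as not related to the device system. A note in the same cell says: "Physician and study subject induced injury will be recorded, but will not be included as adverse events in the endpoint analysis of the study". Its examples are "auto accident causing lead/header dysfunction, or inadvertent cutting of lead insulation by physician during the implantation procedure". The note names no exception and does not mention Section 12.1.2. Perforation and tamponade appear in the lead-related column instead.

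**Section 7** has a similar exclusion in narrower words. What it leaves out is "Investigator and study subject induced device dysfunctions".

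**The concern.** One rule says that cause does not matter for three named events. The other excludes by cause, and its key word is *injury*. A pneumothorax caused by the implanter's venous access, and needing an invasive procedure, meets Section 12.1.2 and also fits the literal words of the note. By the same wording the note would reach a physician-induced perforation or tamponade, although these sit in another column.

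This matters because the primary test is single-arm, against a fixed figure: the lower one-sided 95% bound on the five-year rate must exceed 92.5%. Every event left out raises the estimate. There is no comparison arm in which the same omission could offset it, so an error here runs in one direction, towards success.

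**Working it through.** **The texts side by side, for a physician-induced pneumothorax with a qualifying outcome**

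| Text | Literal answer |
|---|---|
| 12.1.2 | In, whatever the cause or timing |
| 12.3.1 | In, because endpoint events are those meeting 12.1.2 |
| Table 18.2-1 note | Out, as physician-induced injury |
| Section 7 | Not addressed: it excludes induced device dysfunctions, and a pneumothorax is an injury to the patient |

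Three of the four texts are compatible. Only the note, read at full width, conflicts.

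**Scale if the note were applied literally**

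The plan has no figure to reproduce here: it gives no rate for these events, and the sample size inputs in Section 12.1.4 are redacted.

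From the documents: n = 1,780 (Section 8.1); goal 92.5% and one-sided 5% level (Section 12.1.3). Assumed: five-year attrition of 35% (range 20% to 50%); a fraction r of subjects whose qualifying early event is omitted; every disputed event omitted; constant hazards.

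Let C be the correctly counted rate. Then:

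- Rate estimated after omission: S = C/(1 − r)
- Event hazard h = −ln(S)/5; censoring hazard c = −ln(1 − attrition)/5
- Greenwood variance of ln S: V = h(exp(5(h + c)) − 1)/((h + c)n); se = S√V
- P(false success) = Φ((S − 0.925)/se − 1.645)

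One case in full, with C = 0.925, r = 0.5% and 35% attrition:

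- S = 0.925/0.995 = 0.9296
- h = 0.01459, c = 0.08616, h + c = 0.10075
- V = 0.01459 × (exp(0.5037) − 1)/(0.10075 × 1,780) = 0.0000533
- se = 0.9296 × 0.00730 = 0.00679
- (0.92965 − 0.925)/0.00679 = 0.685, and Φ(0.685 − 1.645) = 16.9%

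| r omitted (subjects of 1,780) | S when C = 92.5% | P, C = 92.5% | P, C = 92.0% |
|---|---|---|---|
| 0 | 92.50% | 5.0% | 1.0% |
| 0.1% (about 2) | 92.59% | 6.5% | 1.3% |
| 0.25% (about 4) | 92.73% | 9.5% | 2.1% |
| 0.5% (about 9) | 92.96% | 16.9% | 4.5% |
| 1.0% (about 18) | 93.43% | 41.2% | 15.5% |

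Sensitivity at C = 92.5%:

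- **Attrition of 20% and 50%:** 6.6% and 6.4% at r = 0.1%; 17.9% and 15.7% at r = 0.5%.
- **Log-log bound** (Section 12.3.1 names no formula), 35% attrition: 6.5%, 9.5%, 16.3% and 37.7% for the four non-zero rows.
- **Simulation**, 10,000 Kaplan-Meier runs per row, 35% attrition: the plain Greenwood bound gives 5.9% with no omission, then 8.0%, 11.1%, 19.1% and 42.0%; the log-log bound gives 4.5%, then 6.3%, 8.8%, 16.0% and 36.8%.

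The plain bound is thus slightly liberal before anything is omitted. That part is not due to the note, and figures close to 5% in the table should be read as approximate.

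**The case against.** The case for leaving the text alone is strong, and most of it stands.

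- **Section 12.1.2 is the natural governing rule.** Setting cause aside for three named events already covers a physician cause, and Section 12.3.1 defines endpoint events by 12.1.2 alone. The note is general text in a table of example causes.
- **The note looks like Section 7 restated.** It has the same record-but-exclude structure and shares the cut-insulation example. Its other example is also lead or header dysfunction.
- **Sharing a cell is not an exclusion.** A reader might infer that pneumothorax is excluded because it is listed beside the note. The table does not support that: the same cell lists infection and lead under-insertion at implant, and Section 12.1.2 admits both when the CEC attributes them to structural failure.
- **Sites report the event under either reading**, and an independent committee decides inclusion. Its charter is not among the documents and may settle the question.

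What this does not remove is the wording. The note says *injury*, the word Section 12.1.2 itself uses for a qualifying outcome. Section 12.1.2 closes by sending the reader to Section 18 for further explanation, where the note sits. The revision history records that Table 18.2-1 was updated in the current version, so it is hard to set aside as leftover text. The intended order has to be inferred, because nothing states it.

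**Conclusion.** The conflict is real but small. Applied literally, the note would drop events that Section 12.1.2 counts. The most likely explanation is that *injury* is broader than was intended and that 12.1.2 governs.

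A reader might infer that the plan carries a false-success risk of up to 41%. The documents do not support that. The figure needs an assumed 1.0% of subjects with an omitted event, omission of every disputed event, and a counted rate of exactly 92.5%. With 0.1% to 0.5% of subjects affected, false success at that boundary goes from 5% to about 6.5% to 17%. At a counted rate of 92.0% it is 1.3% to 4.5%, below the nominal level. At 91.5%, 0.5% omitted gives 0.8% and 1.0% omitted gives 4.0%. If the CEC applies Section 12.1.2 as written, there is no effect.

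Severity: minor. Confidence is high that the two texts conflict as worded. The consequence is conditional on how the CEC reads the note, and its size cannot be known from the documents.

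**What to change.** In the Table 18.2-1 note:

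1. Replace *induced injury* with Section 7's *induced device dysfunctions*.
2. Add one sentence saying that Sub-section 12.1.2 governs endpoint inclusion, including its rule that pneumothorax, perforation and cardiac tamponade count whatever the cause.

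Sections 7 and 12.1.2 can stay as they are. No extra analysis is needed, since Section 12.3.2 already says of the events contributing to the endpoint that "The individual adverse event rates and 95% upper confidence bounds will be provided".

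The cost is one phrase and one sentence, with no new data. The downside is that the reported complication-free rate may be slightly less favourable than under the exclusion reading.
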